The increase in serum phosphorus observed after treatment with pemigatinib was exposure-dependent and followed a sigmoid relationship. A population Emax model of pemigatinib AUC and maximal serum phosphate change from baseline was developed. For those participants treated with pemigatinib 13.5 mg who did not develop hyperphosphatemia, AUC for pemigatinib 18 mg was estimated using a linear exposure relationship. Maximal serum phosphate change from baseline for each individual was then estimated using a population model. The maximal serum phosphate after treatment with pemigatinib 18 mg was calculated by adding the baseline of serum phosphate. The simulation suggested that the serum phosphate would increase above 5.5 mg/dL after treatment with pemigatinib 18 mg for the participants treated with pemigatinib 13.5 mg who did not develop hyperphosphatemia.

Figure 2: Comparison of Steady State Exposures for Pemigatinib 13.5 mg QD Between Subjects With Nonhyperphosphatemia and Hyperphosphatemia

AUCss = area under the curve at steady state; Css, min = minimum blood plasma concentration at steady state; HP = hyperphosphatemia.

Any participant who does not reach the target serum phosphate level of  $> 5.5$  mg/dL at any time during Cycle 1, and who is compliant with taking study drug and does not experience an ongoing Grade 2 or higher treatment-related AEs, will increase the daily dose to 18 mg starting at Cycle 2 Day 1. Participants who are titrated up to 18 mg QD will begin the next cycle at the new dose level and must agree to all Cycle 1 assessments (PK and safety assessments [hematology and blood chemistry]). Up-titration may occur no earlier than on Day 1 of Cycle 2, so that participants are observed for phosphate level and AEs at least for 1 cycle.

For participants who are up-titrated from 13.5 mg to 18 mg, a maximum of 2 dose level reductions is also recommended: 18 mg can be decreased to 13.5 mg, and if additional dose reduction is required, participants can decrease to 9 mg. Dose reductions below 9 mg are not allowed."

[figure not shown]
A CYP3A4-mediated drug-drug interaction study (INCB 54828-104) indicated there is evidence of a clinically significant effect on pemigatinib exposure when co-administered with a potent CYP3A4 inhibitor, itraconazole (increased pemigatinib AUC by 88%) or

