**\*All of the following criteria must be met in order to increase dose level beginning at cycle 2**

- Participant does not reach the target serum phosphate level of > 5.5 mg/dL at any time during Cycle 1.
- Patient is compliant with taking study drug.
- Patient does not experience an ongoing Grade 2 or higher treatment-related AEs during cycle 1.
- If dose level escalated, please remember to report as modified treatment in Rave.

7.2 If all criteria for dose increase are not met patient will remain at dose level 0. Dose may be increased at a future cycle if patient meets criteria. Note: If dose escalated, please remember to report as modified treatment in Rave.

7.3 Patients can be instructed in Pemigatinib administration techniques and granted treatment independence with nursing staff approval.

7.4 For this protocol, the patient must return to the consenting ACCRU institution for evaluation during treatment and during observation (Active Monitoring Phase) according to the table in Section 4.0.

7.5 Patients will be required to keep a medication diary for Pemigatinib using the diary in appendix III. Sites will be required to upload medication diary to RAVE at the end of each cycle.

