#### 8.2 Dose Modifications

Use the NCI Common Terminology Criteria for Adverse Events (CTCAE) Version 5.0 dated November 27, 2017* unless otherwise specified		
ADVERSE EVENT	AGENT	ACTION
Chemistry		
AST and/or ALT $> 5.0 \times$ ULN and/or ALP $> 5.0 \times$ ULN  Note: In patients with liver or bone metastasis-related elevations at baseline, contact sponsor-investigator to discuss clinical management and possible dose reductions.	Pemigatinib	
Step 1: Hold/Delay Pemigatinib up to 2 weeks (14 days) until the toxicity has resolved to <math>\leq</math> Grade 1 except by written approval from the sponsor-investigator.
 
Step 2: If assessed by the investigator as not related or unlikely related to Pemigatinib, then restart Pemigatinib at same dose; monitor as clinically indicated.
 
Step 2: If assessed by the investigator as possibly, probably or definitely related to Pemigatinib, then restart Pemigatinib at the next lower dose level; monitor as clinically indicated.

ANC is $0.5 \times 10^9/L$ to $< 1.0 \times 10^9/L$ (grade 3)  Platelet count is $50 \times 10^9/L$ to $< 75 \times 10^9/L$ (grade 2)	Pemigatinib	
Step 1: Interrupt study drug up to 2 weeks (14 days) until the toxicity has resolved to Grade 1 or pretherapy baseline.
 
Step 2: Restart study drug at same dose and monitor as clinically indicated.
 
*If neutropenia is rapidly reversible after stopping study drug, subjects will be allowed to stay on their dose as long as ANC <math>> 1.0 \times 10^9/L</math>.

Grade 4 ANC ( $< 0.5 \times 10^9/L$ )  Grade 3 ANC with an oral temperature of at least $38.5^{\circ}C$ OR with Grade 3 infection  Platelet count is $< 50 \times 10^9/L$ (grade 3 or 4)	Pemigatinib	
Step 1: Interrupt study drug up to 2 weeks (14 days) until resolved to Grade 1.
 
Step 2: If assessed as related to study drug, restart study drug at next lower dose level, except if Grade 4 neutropenia resolves in <math>\leq 7</math> days, in which case restart at the same dose.

Other Toxicities		
Any Grade 1 or other Grade 2 toxicity	Pemigatinib	Continue Pemigatinib; treat the toxicity and monitor as clinically indicated.

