- Within every given cycle, an Pemigatinib dose hold/delay is permitted, with a maximum duration of no more than 14 total days in each cycle (regardless of whether such 14 total days within any given cycle are consecutive or cumulative days).
- In all cases, a patient may receive no more than 21 total doses of Pemigatinib in a single cycle.
- Dose re-escalation only allowed after discussion with study PI and sponsor, if clinically indicated.
- If dosing is delayed greater than 42 days, patient should be removed from treatment, and proceed to event monitoring.

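### For a patient cut to 9 mg in Cycle 1 for a related event that has since resolved, Sections 1.5, 7.1 and 7.2 give a different dose from Sections 8.2 and 8.3

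*Combined protocol and SAP*

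**What the plan says.** All patients start at level 0, 13.5 mg daily (Section 8.1). Section 7.1 lists 18 mg for cycles 2 to 35, subject to three conditions:

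- Phosphate: "Participant does not reach the target serum phosphate level of > 5.5 mg/dL at any time during Cycle 1".
- Compliance: "Patient is compliant with taking study drug".
- Toxicity: "Patient does not experience an ongoing Grade 2 or higher treatment-related AEs during cycle 1".

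Section 1.5 repeats the conditions in mandatory form. Of a participant who meets them it says: "will increase the daily dose to 18 mg starting at Cycle 2 Day 1".

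Section 7.2 covers those who fail: "If all criteria for dose increase are not met patient will remain at dose level 0". It then permits an increase in a later cycle if the criteria are met.

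Section 8.2 sets the response to toxicity. For its more severe hematologic events the drug is interrupted until recovery, and then: "If assessed as related to study drug, restart study drug at next lower dose level, except if Grade 4 neutropenia resolves in". That exception, which returns the patient to the same dose, applies when recovery takes no more than 7 days. Related liver enzyme elevations above 5 times the upper limit, and other related Grade 3 events that are clinically significant and not manageable by supportive care, also restart one level down. From level 0 that is level -1, 9 mg.

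Section 8.3 adds: "Dose re-escalation only allowed after discussion with study PI and sponsor, if clinically indicated". Section 8.1 refers the reader to Section 7.1 for escalation and makes no exception for reduced patients.

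**The concern.** The toxicity condition turns on the word *ongoing*. An event that led to a reduction and then resolved is no longer ongoing, and no other condition asks whether the dose was held or reduced. A site that follows Sections 7.1 and 1.5 would raise the dose to 18 mg. A site that follows Sections 8.2 and 8.3 would keep the patient at 9 mg unless the PI and the sponsor had been consulted. Nothing says which section prevails.

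The phosphate condition adds to the difficulty. Section 1.5 says that the phosphate rise depends on exposure, and it describes up-titration for participants without hyperphosphatemia while on 13.5 mg. Section 7.1 does not carry over that reference dose, so low phosphate after an interruption or on 9 mg counts the same as low phosphate on uninterrupted 13.5 mg.

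What is at stake is patient safety and uniform treatment across sites. The Simon design, its error rates and the sample size do not depend on this point.

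**Working it through.** There is no stated figure to reproduce. The check follows one patient through each section and then gauges how many patients could be affected.

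**Step 1. The patient.** Starts on 13.5 mg. On Day 8 the platelet count is below 50 x 10^9/L, judged related. Under Section 8.2 the drug is interrupted, the count recovers to Grade 1, and the drug restarts at 9 mg. Phosphate never exceeds 5.5 mg/dL.

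**Step 2. Is the timing possible?** A hold may last up to 14 days and the cycle may be extended to absorb it: 21 + 14 = 35 days, the maximum in Section 8.3. Hold, recovery and restart can all fall within Cycle 1.

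**Step 3. The Section 7.1 conditions.**

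| Condition | Result |
|---|---|
| Phosphate never above 5.5 mg/dL in Cycle 1 | Met |
| Compliant (undefined; nothing makes a protocol-directed hold non-compliance) | Met |
| No ongoing related event of Grade 2 or higher (read as still present when the decision is made) | Met |

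With the event still present, the third condition fails. With phosphate above 5.5 mg/dL at any time in Cycle 1, the first fails.

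**Step 4. The dose at Cycle 2 Day 1, by section.**

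| Section | Dose |
|---|---|
| 8.2 | 9 mg, the level just assigned |
| 7.1 with 1.5, criteria met | 18 mg; 18 / 9 = 2 times the assigned dose, two levels up |
| 8.3 | Any re-escalation only after consultation |
| 7.2, if any criterion fails | Level 0, 13.5 mg; 13.5 / 9 = 1.5 times the assigned dose |

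The last row needs no particular reading of *ongoing*. Any patient at level -1 who fails a criterion is told to remain at a level that he or she no longer occupies.

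**Step 5. The later-cycle sentence in Section 7.2.** The phosphate and toxicity criteria are both worded for Cycle 1. On that wording a patient who exceeded 5.5 mg/dL in Cycle 1 can never meet the phosphate criterion later, and one who did not will always meet it, whatever later values show.

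**Step 6. How many patients?** Table 13, continuous 13.5 mg: hyperphosphatemia in 14 of 16, so 16 - 14 = 2 without it. 2 / 16 = 12.5%, Clopper-Pearson 95% interval 1.6% to 38.3%. Applied to the maximum accrual of 24: 24 x 0.125 = 3, with a range of about 0.4 to 9.2. Table 13 counts events at any time on treatment, so the share below target in Cycle 1 alone could be higher. Of these patients, only those also reduced in Cycle 1 for an event that then resolved meet the conflict. The documents give no rate for that.

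**Step 7. Direction of the phosphate relation.** On continuous dosing, 8 - 4 = 4 of 8 (50%) at 9 mg had no hyperphosphatemia, against 2 of 16 (12.5%) at 13.5 mg. This fits Section 1.5's account that phosphate follows exposure. It shows direction only: the groups are defined by dose regimen and followed over all treatment, not patients who started on 13.5 mg and were cut during Cycle 1.

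**The case against.** The best defence reads the sections together. Section 7.1 states necessary conditions, the later-cycle sentence of Section 7.2 is permissive, and Section 8.3 adds a restriction for anyone previously reduced. Section 1.5 speaks of moving from 13.5 mg to 18 mg, and Sections 7.1 and 7.2 start from level 0, so a direct step from 9 mg to 18 mg may never have been intended. The toxicity condition could also mean ongoing at any time in Cycle 1, which would exclude the patient in the example.

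This softens the clash but does not remove it. Section 1.5 is worded as an instruction, not a permission. No section says whether a first move to 18 mg from 9 mg is re-escalation. The any-time reading leaves the word *ongoing* with little to do. The Section 7.2 contradiction for patients at level -1 stands on any reading.

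A reader might infer more than the documents support:

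- **Holds without reduction.** A patient held and restarted at the same dose (for example, Grade 4 neutropenia that resolves within 7 days) may meet the Section 7.1 criteria. There was no reduction, so Section 8.3 is not engaged, and Section 8.2 does not in general bar a later increase. This is a gap, not a contradiction.
- **Serious toxicity in general.** Other clinically significant Grade 4 events lead to permanent discontinuation, and patients held for high phosphate fail the phosphate condition.
- **18 to 13.5 and back to 18 mg.** This is plainly re-escalation, and Section 8.3 already governs it.
- **A prohibition in Section 8.3.** That section requires consultation; it does not forbid re-escalation.
- **A rule that steers patients with early toxicity to the top dose.** The Table 13 contrast cannot be turned into a multiple for this trial, for the reason in Step 7. A patient reduced in Cycle 1 has also already taken 13.5 mg, and any value above 5.5 mg/dL in that time disqualifies. Section 1.4 reports no monotherapy dose-limiting toxicity, with continuous dosing up to 20 mg.

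**Conclusion.** The point holds for patients reduced to level -1 in Cycle 1. If the event has resolved and phosphate stayed at or below 5.5 mg/dL, the literal text gives 18 mg in one place and 9 mg, with consultation before any increase, in another. If such a patient does not qualify, the text gives 13.5 mg in one place and 9 mg in another. The first conflict assumes that *ongoing* means still present at the decision and that a directed hold is not non-compliance. The second needs neither assumption.

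The number affected is probably small: some part of about 3 in 24, with wide uncertainty and no documented reduction rate. The reason to act is that the text bears on safety and is cheap to correct.

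**What to change.** The sponsor should reconcile Sections 1.5, 7.1, 7.2, 8.2 and 8.3 so that each patient has one written dose. The text should state:

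- which section governs after a Cycle 1 reduction, and whether a hold without reduction matters;
- whether a first move to 18 mg from level -1 counts as re-escalation;
- what *ongoing* and *compliant* mean for this decision;
- on what dose, and in which cycle, the phosphate criterion is assessed, including for the later increases that Section 7.2 permits;
- what Section 7.2 means for a patient already at level -1.

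The choice of clinical rule is the sponsor's, and none is proposed here. The cost is a wording amendment with no added visits or patients. Depending on the rule chosen, a few dose decisions may be deferred or referred to the PI.

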## 8.0 Dosage Modification Based on Adverse Events

For all adverse events reported in this study considered by the investigator as possibly, probably

or definitely related to Pemigatinib, the following dose modification guidance should be applied.

Adverse events considered by the investigator as definitely related to something other than Pemigatinib, or transient ( $\leq 72$  hours) abnormal laboratory values without associated signs or symptoms deemed clinically significant by the investigator, may be exempt from dose-reduction rules unless otherwise requested or required by the sponsor-investigator.

**ALERT:** ADR reporting may be required for some adverse events (See Section 10)

#### 8.1 Dose Level Reductions (if needed for management of potential adverse event)

Dose Level	Pemigatinib
1	18 mg PO QD
0	13.5 mg PO QD
-1	9 mg PO QD

\* All patients are scheduled to initiate Pemigatinib at Dose Level 0.

See section 7.1 for dose escalation information.

Note: If dose escalated, please report as modified treatment in Rave.

#### 8.2 Dose Modifications

Use the NCI Common Terminology Criteria for Adverse Events (CTCAE) Version 5.0 dated November 27, 2017* unless otherwise specified		
ADVERSE EVENT	AGENT	ACTION
Chemistry		
AST and/or ALT $> 5.0 \times$ ULN and/or ALP $> 5.0 \times$ ULN  Note: In patients with liver or bone metastasis-related elevations at baseline, contact sponsor-investigator to discuss clinical management and possible dose reductions.	Pemigatinib	
Step 1: Hold/Delay Pemigatinib up to 2 weeks (14 days) until the toxicity has resolved to <math>\leq</math> Grade 1 except by written approval from the sponsor-investigator.
 
Step 2: If assessed by the investigator as not related or unlikely related to Pemigatinib, then restart Pemigatinib at same dose; monitor as clinically indicated.
 
Step 2: If assessed by the investigator as possibly, probably or definitely related to Pemigatinib, then restart Pemigatinib at the next lower dose level; monitor as clinically indicated.

ANC is $0.5 \times 10^9/L$ to $< 1.0 \times 10^9/L$ (grade 3)  Platelet count is $50 \times 10^9/L$ to $< 75 \times 10^9/L$ (grade 2)	Pemigatinib	
Step 1: Interrupt study drug up to 2 weeks (14 days) until the toxicity has resolved to Grade 1 or pretherapy baseline.
 
Step 2: Restart study drug at same dose and monitor as clinically indicated.
 
*If neutropenia is rapidly reversible after stopping study drug, subjects will be allowed to stay on their dose as long as ANC <math>> 1.0 \times 10^9/L</math>.

Grade 4 ANC ( $< 0.5 \times 10^9/L$ )  Grade 3 ANC with an oral temperature of at least $38.5^{\circ}C$ OR with Grade 3 infection  Platelet count is $< 50 \times 10^9/L$ (grade 3 or 4)	Pemigatinib	
Step 1: Interrupt study drug up to 2 weeks (14 days) until resolved to Grade 1.
 
Step 2: If assessed as related to study drug, restart study drug at next lower dose level, except if Grade 4 neutropenia resolves in <math>\leq 7</math> days, in which case restart at the same dose.

Other Toxicities		
Any Grade 1 or other Grade 2 toxicity	Pemigatinib	Continue Pemigatinib; treat the toxicity and monitor as clinically indicated.
Any other Grade 3 toxicity, if clinically significant and not manageable by supportive care.	Pemigatinib	
Step 1: Hold/Delay Pemigatinib up to 2 weeks (14 days), until toxicity resolves to <math>\leq</math> Grade 1.
 
Step 2: If assessed by the investigator as not related or unlikely related to Pemigatinib, then restart Pemigatinib at same dose; monitor as clinically indicated.
 
Step 2: If assessed by the investigator as possibly, probably or definitely related to Pemigatinib, then restart Pemigatinib at the next lower dose level; monitor as clinically indicated.

Any recurrent Grade 3 toxicity after 2 dose reductions.	Pemigatinib	Permanently discontinue Pemigatinib and initiate post-treatment follow-up per Protocol. (Exceptions require written approval of sponsor-investigator.)

Any other Grade 4 toxicity, if clinically significant	Pemigatinib	Permanently discontinue Pemigatinib and initiate post-treatment follow-up per Protocol.
---	-------------	--

\* Located at [REDACTED]

\*\* The following describe actions in the Action column:

- Hold/Delay = Treatment can be made up (see Section 8.3) as part of this cycle;
- Discontinue = Treatment is totally stopped.

Hyperphosphatemia is an expected on-target pharmacologic effect of FGFR inhibition. Hyperphosphatemia should be managed with diet modifications, phosphate binders and diuretics, or a dose reduction per the recommendations in the below table:

Recommended Approach for Hyperphosphatemia Management			
Serum Phosphate Level	Supportive Care	Guidance for Interruption/Discontinuation of Pemigatinib	Guidance for Restarting Pemigatinib
> 5.5 mg/dL and $\leq$ 7 mg/dL	Initiate a low-phosphate diet.	No action.	Not applicable.
> 7 mg/dL and $\leq$ 10 mg/dL	Initiate/continue a low-phosphate diet and initiate phosphate-binding therapy once serum phosphate level is > 7 mg/dL.  Monitor serum phosphate at least twice a week and adjust the dose of binders as needed; continue to monitor serum phosphate at least twice a week until return to normal range.	If serum phosphate level continues to be > 7 mg/dL and $\leq$ 10 mg/dL with concomitant phosphate-binding therapy for 2 weeks, or if there is recurrence of serum phosphate level in this range, hold/delay Pemigatinib for up to 2 weeks	Restart Pemigatinib at the same dose when serum phosphate is < 7 mg/dL.  If serum phosphate level recurs at > 7 mg/dL, restart Pemigatinib with dose reduction .

> 10 mg/dL	
Continue to maintain a low-phosphate diet, adjust phosphate-binding therapy, and start/continue phosphaturic agent.
 
Continue to monitor serum phosphate at least twice a week until return to normal range.
	
If serum phosphate level is > 10 mg/dL for 1 week following phosphate-binding therapy and low phosphate diet, hold/delay Pemigatinib.
 
If there is recurrence of serum phosphate level in this range following 2 dose reductions, permanently discontinue Pemigatinib.
	
Restart Pemigatinib at reduced dose with phosphate binders when serum phosphate is < 7 mg/dL.

------------	---	--	--

\*\* The following describe actions above:

- Hold/Delay = Treatment can be made up (see Section 8.3) as part of this cycle;
- Discontinue = Treatment is totally stopped.

8.3 For reasons that are consistent with the Dose Modifications outlined above in Section 8.2, Pemigatinib treatment that is held/delayed for purpose of adverse event management can be “made up” within a given cycle:

- The scheduled duration of a cycle is 21 days (3 weeks).
- For purpose of accommodating an established Pemigatinib dose hold/delay, the number of days in any given cycle may be increased up to 14 total days, in order to accommodate a maximum cycle length of 35 days (5 weeks).

Note: The purpose of this guidance is not to accommodate re-dosing in the absence of an established Pemigatinib dose hold/delay. For example, inadvertently missed or vomited doses of Pemigatinib are not to be “made up” within the cycle, but rather should be omitted from the cycle (and noted as such in the patient-completed medication diary).

- Within every given cycle, an Pemigatinib dose hold/delay is permitted, with a maximum duration of no more than 14 total days in each cycle (regardless of whether such 14 total days within any given cycle are consecutive or cumulative days).
- In all cases, a patient may receive no more than 21 total doses of Pemigatinib in a single cycle.
- Dose re-escalation only allowed after discussion with study PI and sponsor, if clinically indicated.
- If dosing is delayed greater than 42 days, patient should be removed from treatment, and proceed to event monitoring.

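### The 7-day same-dose exception for Grade 4 neutropenia in Section 8.2 has no fever or infection condition, so read literally febrile Grade 4 is treated more leniently than febrile Grade 3

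*Combined protocol and SAP*

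**What the plan says.** Two adjacent rows of the table in Section 8.2 (Dose Modifications) deal with neutropenia.

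- **Plain Grade 3 row** (ANC 0.5 to below 1.0 × 10⁹/L). Treatment is interrupted for up to 14 days, then: "Restart study drug at same dose and monitor as clinically indicated". A note in the same row adds: "If neutropenia is rapidly reversible after stopping study drug, subjects will be allowed to stay on their dose as long as ANC" is above 1.0 × 10⁹/L.
- **Grade 4 / complicated row.** The triggers are Grade 4 ANC (below 0.5 × 10⁹/L, with no qualifier), "Grade 3 ANC with an oral temperature of at least" 38.5 °C or with Grade 3 infection, and platelets below 50 × 10⁹/L. Step 1 interrupts treatment for up to 14 days until Grade 1. Step 2 reads "If assessed as related to study drug, restart study drug at next lower dose level", followed by "except if Grade 4 neutropenia resolves in" 7 days or less, "in which case restart at the same dose".

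Three other provisions bear on the reading. Section 8.0 says that transient (72 hours or less) "abnormal laboratory values without associated signs or symptoms deemed clinically significant by the investigator, may be exempt from dose-reduction rules". Section 8.2 has a catch-all row for "Any other Grade 3 toxicity, if clinically significant and not manageable by supportive care", which leads to a hold and, if related, a reduction. A parallel catch-all row for other clinically significant Grade 4 toxicity leads to permanent discontinuation.

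**The concern.** Within the same table, adding fever or Grade 3 infection to Grade 3 ANC moves the patient from resuming at the current dose to resuming one level lower. The protocol therefore already treats those complications as grounds for reduction. The Grade 4 exception drops that distinction. It asks how deep the neutropenia was and how long it lasted, but not whether the patient was febrile or infected. If sites follow the text, the more severe febrile event can get the lighter dose action.

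What is at stake is the restart dose of an individual patient, and consistency between sites in a multicenter study. An up-titrated patient could resume at 18 mg after febrile Grade 4 neutropenia. This is a patient-safety wording point and has no bearing on the efficacy inference.

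**Working it through.** The plan states no figure to reproduce here. The check is to put each case through the written rule, look for text that overrides the result, and then size the consequence.

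**Step 1. The rule applied to related events, with no separately qualifying infection**

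| Case | ANC (× 10⁹/L) | Temperature ≥38.5 °C | Back to Grade 1 in ≤7 days | Restart dose as written |
|---|---|---|---|---|
| a | Grade 3 (0.5 to <1.0) | No | Either | Same (plain Grade 3 row) |
| b | Grade 3 | Yes | Either | One level lower; no exception |
| c | Grade 4 (<0.5) | No | Yes | Same (exception) |
| d | Grade 4 | Yes | Yes | **Same (exception)** |
| e | Grade 4 | Either | No | One level lower |

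From a to b, fever turns same dose into reduction. From c to d, fever changes nothing. Comparing b with d for events of equal short duration, the deeper febrile neutropenia keeps its dose and the shallower one is reduced. Beyond 7 days (case e against case b) both are reduced, so the inversion is confined to case d.

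The table takes *resolves* to mean recovery to Grade 1, as in Step 1 of the same row. If it meant only leaving Grade 4, more patients would fall in case d.

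**Step 2. Text that might override case d**

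- The fever trigger is attached to Grade 3 only, and the table defines Grade 3 as 0.5 to below 1.0 × 10⁹/L, so it does not apply while ANC is below 0.5.
- The Section 8.0 laboratory exemption can only remove a reduction. It cannot add one.
- The rapid-reversibility note belongs to the plain Grade 3 row and also points to keeping the dose.
- The catch-all rows cover other toxicities, and Grade 4 ANC has its own row. They may catch an accompanying infection graded as a separate event. Whether CTCAE v5.0 grades Grade 4 ANC with fever alone as a separate event cannot be settled from these documents.

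None of these clearly overrides case d.

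**Step 3. Size for an affected patient** (dose levels from Section 8.1)

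- 18 mg to 13.5 mg: 1 − 13.5/18 = 0.25, a 25% lower dose.
- 13.5 mg to 9 mg: 1 − 9/13.5 = 0.33, a 33% lower dose.

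**Step 4. Frequency**

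No rate of febrile Grade 4 neutropenia can be derived. The available indications are indirect.

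- Table 13 (Section 1.4) lists terms reported in at least 10% of 106 monotherapy patients. The term neutropenia is absent.
- Neutropenia is also absent from the at-least-10% lists for Studies 201 and 202 in Section 15.17.
- Table 14 (combinations), term neutropenia: gemcitabine/cisplatin 0/1 + 3/7 and docetaxel 3/7 give 6/15. Pembrolizumab 0/17 + 0/6 and trastuzumab 0/6 give 0/29. The total is 6/44 = 13.6%, matching the table.

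These counts are per preferred term, so they do not cap events coded differently. Section 10.52, for example, solicits a decreased neutrophil count as its own term. The Table 14 split reflects the combination partners and says little about pemigatinib alone.

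**The case against.** The strongest reply is that this is a drafting slip of very small reach. The patient must have Grade 4 neutropenia that is drug-related and accompanied by a temperature of at least 38.5 °C, have no infection that another row would catch, and recover to Grade 1 within a week. A patient still febrile as ANC climbs back through 0.5 to below 1.0 × 10⁹/L would also meet the complicated Grade 3 trigger, which has no exception. If CTCAE v5.0 grades fever with neutropenia as its own event, a catch-all row might apply. Section 8.0 describes the rules as guidance. Section 16.42 commits the team to reviewing every Grade 4 and 5 adverse event, and Section 10.4 requires 24-hour notification of Grade 3–5 events with hospitalization of at least 24 hours.

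Most of this stands, and it sets the weight of the point. It does not remove the point:

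- The recovery-through-Grade-3 argument leaves one course of illness with two conflicting instructions, which itself needs clarifying.
- The Grade 3 catch-all row applies only when supportive care fails.
- Review and expedited reporting make the event visible but do not set the restart dose.

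A reader might infer that the drafters meant febrile Grade 4 patients to keep their dose. The documents do not support that: the use of fever and Grade 3 infection in the Grade 3 rules suggests that uncomplicated Grade 4 was meant. A reader might also infer that every infected Grade 4 patient escapes reduction. That too goes further than the text, because the catch-all rows may govern a separate, clinically significant infection.

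**Conclusion.** The point holds as a minor wording defect. As written, the exception gives an inverted dose action for one narrow case: related Grade 4 ANC with fever of at least 38.5 °C, back to Grade 1 within 7 days, with no separately qualifying infection. The size is one dose level for the patient concerned (25% or 33%).

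The event is likely to be very rare on monotherapy, and with a maximum accrual of 24 nothing in the documents supports expecting even one such patient. That is a judgement, not an estimate. A reader might cite the Study 101 frequency tiers in Section 15.17, which go below 1% and omit neutropenia, as proof of rarity. They are poor evidence, because they also omit terms that are common in Table 13, such as anaemia (20.8%), dysgeusia (21.7%) and vomiting (17.9%).

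The conclusion rests on a literal reading of Step 2, on taking resolution to mean recovery to Grade 1, and on no other row clearly overriding the exception. It does not touch the 36-week response endpoint, the two-stage decision rule or the sample size.

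**What to change.** Reword the exception only. In Step 2 of the Grade 4 / complicated row, after the mention of Grade 4 neutropenia, insert: *without an oral temperature of at least 38.5 °C and without Grade 3 or higher infection*. The 7-day limit and the same-dose action then apply to uncomplicated Grade 4 neutropenia, and a related febrile or infected case falls to the default reduction. The row's triggers can stay as they are. The catch-all rows continue to govern any separate clinically significant infection, including discontinuation for Grade 4.

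The cost is one clause, which can go into any routine amendment, and an occasional extra one-level reduction.

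The table gives no general action when a reduction is called for in a patient already at 9 mg, the lowest level allowed. That affects every reduction row and should be raised separately if at all, since a rule placed only in this row would leave the others silent.
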